7.2 Study Conduct

7.2.1 Accrual

The accrual pattern will be summarized per country, investigational site and per month for all enrolled subjects. Randomization date, first dosing date, country, investigational site will be presented in a by subject listing of accrual.

7.2.2 Relevant Protocol Deviations

The relevant Protocol Deviations will be summarized for all randomized subjects, by treatment group and overall. The following programmable deviations from inclusion and exclusion criteria will be considered as relevant protocol deviations. Non-programmable relevant eligibility and on-treatment protocol deviations, as well as significant (both programmable and non-programmable) eligibility and on-treatment protocol deviations will be reported through ClinSIGHT listings.

At entrance:

- Subjects without confirmed SCLC.
- Subject with baseline ECOG PS > 1.
- Subjects without evaluable disease at baseline.
- Subjects who received prior treatment with topotecan or amrubicin,

- Subjects who received less than 4 cycles of platinum-based, first-line chemotherapy without a best overall response (BOR) of a partial or complete response after completion of chemotherapy

On-Study:

- Subjects receiving concurrent anti-cancer therapy (defined as chemotherapy, hormonal immunotherapy, radiation therapy, standard or investigational agents for treatment of SCLC).
- Subject treated differently as randomized (subjects who received the wrong treatment, excluding the never treated).

A subject listing will also be produced.

7.3 Study Population

7.3.1 Subject Disposition

The total number of subjects enrolled (randomized or not randomized) will be presented along with the reason for not being randomized.

Number of subjects randomized but not treated along with the reason will be tabulated by treatment group as randomized. This analysis will be performed on the all randomized population only.

Number of subjects who discontinued study treatment along with corresponding reason will be tabulated by treatment group as treated.

A subject listing for all randomized subjects will be provided showing the subject's randomization date, first and last dosing date, off study date and reason for going off-study. A subject listing for subjects not randomized will also be provided, showing the subject's race, gender, age, consent date and reason for not being randomized.

7.3.2 Demographics and Other Baseline Characteristics

The following baseline characteristics will be summarized by treatment arm as randomized. All baseline presentations identify subjects with missing measurements. Listings will also be provided.

- Age (descriptive statistics).
- Age category (< 65, ≥ 65 - < 75, ≥ 75, ≥ 65).
- Gender, Race/Ethnicity, Region (US/Canada vs. Europe vs. Asia vs. Rest of World).
- Baseline ECOG PS,
- Baseline Weight (kg).
- Baseline LDH (≤ ULN, > ULN)
- Baseline LDH (≤ 2x ULN, > 2x ULN)
- CNS Metastasis (Yes/no)

- Cell type: (SCLC; other)
- Smoking Status (current/former; never smoked; unknown)
- Disease stage: Extensive versus Limited subjects (Source: eCRF)
- All lesions (Investigator Tumor Assessments at Baseline): sites of disease, number of disease sites per subject.
- Target Lesions (Investigator Tumor Assessments at Baseline): Presence of target lesions, site of target lesion, sum of diameters of target lesions.

7.3.3 Medical History

General medical history will be listed by subject and pretreatment events will be tabulated.

7.3.4 Prior Therapy Agent

Prior therapy will be summarized in a single table (Source: CRF).

Prior anti-cancer therapy.

- Line of therapy (First/Unknown)
- Number of cycle of Platinum first line therapy
- Number of cycle of Etoposide as first line therapy
- Number of cycle of Irinotecan as first line therapy
- Best response to 1st line (CR/PR vs. SD vs. PD).
- Primary reason for discontinuation of 1st line therapy
- Time from completion of most recent regimen to treatment (< 3, 3 - 6, > 6 months).
- Prior surgery related to cancer (yes or no).
- Prior PCI (yes or no).
- Prior radiotherapy (yes/no)
- Prior systemic therapy classified by therapeutic class and generic name.

Other Prior therapy:

- Prior/current non-study medication classified by anatomic and therapeutic classes.

Agents and medication will be reported using the generic name. A listing by subject will also be provided.

7.3.5 Baseline Examinations

Subjects with abnormal baseline physical examination will be tabulated by examination criteria and by treatment group.

7.3.6 Discrepancies between IVRS and CRF Stratification Factors

Summary tables (cross-tabulations) by treatment group for stratification factor will be provided to show any discrepancies between what was reported through IVRS vs. CRF data (baseline).

7.4 Extent of Exposure

7.4.1 Administration of Study Therapy

The following parameters will be summarized (descriptive statistics) by treatment group:

- Relative dose intensity (%) using the following categories: < 50%; 50 - < 70%; 70 - < 90%; 90 - < 110%; ≥ 110%.
- Number of doses received (summary statistics).
- Cumulative dose

Duration of treatment will be presented by treatment group using a Kaplan-Meier curve whereby the last dose date will be the event date for those subjects who are off study therapy. Median duration of treatment and associated 95% CI will be provided. Subjects who are still on study therapy will be censored on their last dose date.

A by-subject listing of dosing of study medication (record of study medication, infusion details, dose change) and a listing of batch number will be also provided.

Below table summarizes the key parameters used to calculate dosing data.

Table 7.4.1-1: Administration of study therapy: definition of parameters

	Nivolumab	Topotecan IV	Topotecan Oral	Amrubicin
Dosing schedule per protocol	240mg every 2 weeks	1.5mg/m ² for days 1 to 5 of every 3 weeks cycle	2.3mg/m ² for days 1 to 5 of every 3 weeks cycle	40mg/m ² for days 1 to 3 of every 3 weeks cycle
Dose	Dose is defined as Total Dose administered (mg)	Dose (mg/m²) is defined as Total Dose administered (mg) / Most recent BSA. Dose administered in mg at each dosing date and BSA (computed using recent weight and bsl height) are collected on the CRF.	Dose (mg/m²) is defined as Total Dose administered (mg) / Most recent BSA. Dose administered in mg at each dosing date and BSA (computed using recent weight and bsl height) are collected on the CRF.	Dose (mg/m²) is defined as Total Dose administered (mg) / Most recent BSA. Dose administered in mg at each dosing date and BSA (computed using recent weight and bsl height) are collected on the CRF.
Cumulative Dose	Cum dose is sum of the doses (mg) administered to a subject during the treatment period.	Cum dose (mg/m²) is sum of the doses (mg/m²) administered to a subject during the treatment period.	Cum dose (mg/m²) is sum of the doses (mg/m²) administered to a subject during the treatment period.	Cum dose (mg/m²) is sum of the doses (mg/m²) administered to a subject during the treatment period.
Relative dose intensity (%)	Cum dose (mg) / [(Last dose date - Start dose date + 14) x 240 / 14] x	Cum dose (mg/m²) / [(First dose date in last cycle - Start dose date	Cum dose (mg/m²) / [(First dose date in last cycle - Start dose	Cum dose (mg/m²) / [(First dose date in last cycle - Start dose

Table 7.4.1-1: Administration of study therapy: definition of parameters

	Nivolumab	Topotecan IV	Topotecan Oral	Amrubicin
	100	+ 21) x 7.5 / 21] x 100	date + 21) x 11.5 / 21] x 100	date + 21) x 120 / 21] x 100
Duration of treatment	Last dose date - Start dose date +1	Last dose date - Start dose date +1	Last dose date - Start dose date +1	Last dose date - Start dose date +1

7.4.2 Modifications of Study Therapy

7.4.2.1 Cycle Delays

A cycle will be considered as actually delayed if the delay is exceeding 3 days (i.e., greater than or equal to 4 days from scheduled dosing date) for both nivolumab and topotecan/amrubicin. It is defined as (duration of previous cycle in days -14) for nivolumab (or -21 for topotecan/amrubicin). Cycle delays will be divided into following categories: on-time, 4 - 7 days, 8 - 14 days, 15 - 42 days, > 42 days. Reason for Cycle delay will be retrieved from CRF dosing pages.

Each nivolumab or topotecan/amrubicin infusion can be interrupted and/or the IV infusion rate can be reduced. This information will be retrieved from CRF dosing pages.

The following parameters will be summarized by treatment arm:

- Number of cycle delayed per subject, Length of Delay and Reason for cycle Delay.
- Number of subject with at least one dose infusion interrupted along with reason for the interruptions and number of infusions interrupted per subject.

7.4.2.2 Topotecan/Amrubicin Dose interruptions - IV

Topotecan/amrubicin dose interruption will occur if, on Day 1 to Day 5 of each cycle for topotecan or on Day 1 to Day 3 of each cycle for amrubicin, the subject had an IV infusion interruption. Reason for dose interruption will be retrieved from CRF dosing pages.

7.4.2.3 Dose Reductions/Omissions/Increases

There will be no dose escalations or reductions of nivolumab allowed. Subjects may be dosed no less than 12 days from the previous dose.

Each nivolumab or topotecan/amrubicin infusion can be interrupted and/or the IV infusion rate of nivolumab or topotecan can be reduced. This information will be retrieved from CRF dosing pages.

Dose of topotecan/amrubicin may be modified for toxicity. Subjects may be dosed no less than 14 days from the previous dose. Based on local guideline, providing subjects is not experiencing significant toxicity, increase topotecan IV dosage to a maximum of 2mg/m² per day (3.1mg/m² per day for the oral formulation) in increments of 0.25mg/m² per day (0.4mg/m² per day for oral formulation) is possible.

Per the Protocol, dose levels of topotecan IV are defined as:

- Dose level +2: 2mg/m²
- Dose level +1: 1.75mg/m²
- Dose level 0: 1.5mg/m²
- Dose level -1: 1.25mg/m²
- Dose level -2: 1mg/m²

Per the Protocol, dose levels of Oral topotecan are defined as:

- Dose level +2: 3.1mg/m²
- Dose level +1: 2.7mg/m²
- Dose level 0: 2.3mg/m²
- Dose level -1: 1.9mg/m²
- Dose level -2: 1.5mg/m²

Per Protocol, dose levels of amrubicin are defined as follow:

- Dose level 0: 40mg/m²
- Dose level -1: 35 mg/m²
- Dose level -2: 30mg/m²
- Dose level -3: 25mg/m²

Dose reduction/increase, on Day 1 to Day 5 of each cycle for topotecan or on Day 1 to Day 3 of each cycle for amrubicin, is defined as at least one day with a non zero dose smaller/higher than 1mg/m² for topotecan IV (1.5mg.m² for Topotecan oral and 40mg/m² for amrubicin) and smaller than previous non zero dose (with a CRF reason different from “Dosing Error” for oral topotecan).

Dose Omission: a dose is considered as being omitted during a cycle when less than 5 or less than 3 non zero doses have been reported for Topotecan (unless, for oral topotecan, CRF reason is “Dosing Error”) and for amrubicin, respectively.

Dose ranges for dose levels of Topotecan and amrubicin are-defined in Table below

Table 7.4.2.3-1: Dose Modifications

Dose Range (mg/m ²)			Dose Level
Topotecan IV	Topotecan Oral	Amrubicin	
≥ 1.825	≥ 2.9	NA	Level +2
1.625 – < 1.825	2.5 – <2.9	NA	Level +1
1.375 – < 1.625	2.1 - <2.5	≥ 37.5	Level 0
1.125 – < 1.375	1.7 - <2.1	32.5 – < 37.5	Level -1

Table 7.4.2.3-1: Dose Modifications

Dose Range (mg/m ²)			Dose Level
Topotecan IV	Topotecan Oral	Amrubicin	
< 1.125	1.3 - <1.7	27.5 – < 32.5	Level -2
NA	NA	< 27.5	Level -3

The reason for dose reduction as reported by the investigator will be tabulated for all instances of dose reduction based on the Dose Change CRF page. A category ‘Unknown’ will be defined for all reductions with no reason reported by the investigator.

For Nivolumab and Topotecan, the following will be summarized by treatment group:

- Number of subjects with at least one infusion with IV rate reduced along with the reason of the rate reduction.

The following will be summarized for topotecan and amrubicin subjects:

- Number and percentage of subjects with at least one dose reduction and reason of the dose reduction, number and percentage of subjects with a dose reduction to dose level -1, number and percentage of subjects with a dose reduction to dose level -2
- Number and percentage of subjects with at least one dose increase of topotecan, number and percentage of subjects with a dose increase to dose level +1, number and percentage of subjects with a dose reduction to dose level

[REDACTED]

[REDACTED]

[REDACTED]

[REDACTED]

[REDACTED]

A by-subject listing will accompany the table.

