4.5.2.2 Topotecan

Dose modifications and dose delays for the management of toxicities experienced by individual subjects in Arm B who are receiving topotecan are provided in Table 4.5.2.2-1. In addition, treatment may be delayed for any AE, laboratory abnormality, or intercurrent illness which, in the judgment of the investigator, warrants delaying the dose of study medication.

| Table 4.5.2.2-1: Topotecan Dose Modifications and Delays | |
|--|---|
| Adverse Event | Dose Modification |
| ANC < 1000/mm ³ and/or Platelets < 100,000/mm ³ at Day 1 | Delay treatment until: ANC ≥ 1000/mm ³ Platelets > 100,000/mm ³ |
| Toxicity Grade < 2 during previous cycle | Optional, based on local treatment guidelines: Increase IV topotecan dosage to a maximum of 2 mg/m ² per day in increments of 0.25 mg/m ² per day. Increase oral topotecan dosage to a maximum of 3.1 mg/m ² in increments of 0.4 mg/m ² per day. |
| Grade 4 neutropenia with fever or infection, or of duration ≥ 7 days Grade 3 neutropenia during the preceding cycle persisting after Day 21 Grade 4 thrombocytopenia | Reduce IV topotecan dosage by 0.25 mg/m ² per day. Reduce oral topotecan dosage by 0.4 mg/m ² per day. |
| Grade 3/4 Nonhematologic toxicity, excluding Grade 3 nausea | Reduce IV topotecan dosage by 0.25 mg/m ² per day or discontinue treatment. Reduce oral topotecan dosage by 0.4 mg/m ² per day or discontinue treatment. |
| Treatment delay > 6 weeks | Discontinue treatment |

ANC = absolute neutrophil count

Note: The minimum permissible daily IV topotecan dosage is 1 mg/m²; the minimum daily oral topotecan dosage is 1.5 mg/m².

Criteria to Resume Treatment

Subjects may resume treatment with topotecan when the drug-related AE(s) resolve to Grade ≤ 1 or baseline value, with the following exceptions:

- Treatment can be resumed when ANC ≥ 1000/mm³ and platelets > 100,000/mm³
- Subjects may resume treatment in the presence of Grade 2 fatigue
- Subjects who have not experienced a Grade 3 drug-related skin AE may resume treatment in the presence of Grade 2 skin toxicity
- Drug-related pulmonary toxicity must have resolved to baseline before treatment is resumed.

If the criteria to resume treatment are met, the subject should restart treatment at the next scheduled timepoint per protocol.

If treatment is delayed > 6 weeks (42 days) from the last dose, the subject must be permanently discontinued from study therapy, except as specified in [Section 4.5.3.2](#).

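### SAP 7.4.2.3 counts topotecan dose reductions against the lowest dose level, so no reduction between nominal levels is ever counted

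*SAP*

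**What the plan says.** SAP 7.4.2.3 gives one sentence for both directions of dose change. On the dosing days of a cycle, a reduction or increase is "at least one day with a non zero dose smaller/higher than 1mg/m² for topotecan IV", with 1.5 mg/m² as the oral topotecan reference and 40 mg/m² as the amrubicin reference, "and smaller than previous non zero dose". Oral doses with a recorded dosing error are excluded.

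The same section lists the dose levels. For IV topotecan the bottom of the list is "Dose level -2: 1mg/m²"; for oral topotecan Level -2 is 1.5 mg/m²; for amrubicin 40 mg/m² is Level 0. Table 7.4.2.3-1 then assigns actual doses to levels by ranges.

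The section goes on to plan, for topotecan and amrubicin, the "number and percentage of subjects with a dose reduction to dose level -1", the same for Level -2, the number with any reduction and the reasons. For topotecan it also plans the number with an increase.

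Protocol 4.5.2.2 treats a reduction as a step down from the current dose ("Reduce IV topotecan dosage by 0.25 mg/m ² per day") and says: "The minimum permissible daily IV topotecan dosage is 1 mg/m²". The oral minimum in the same note is 1.5 mg/m².

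**The concern.** The topotecan reference in the counting rule is the protocol's permitted minimum, not the starting dose. A nominal dose that follows the protocol cannot fall below it, so it cannot be a reduction. Amrubicin, in the same sentence, is measured against its starting dose. The two comparators would therefore be summarised side by side under different rules.

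The second clause adds a separate fault. It requires the dose to be smaller than the previous one whichever direction is being counted. Read literally, a genuine step up is never an increase, and a step from Level 0 to Level -1 meets the wording for an increase.

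At stake is the report's account of how topotecan was delivered in the control arm: how many subjects had a reduction, to which level and why, and how many had an increase.

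**Working it through.** **Inputs** (SAP 7.4.2.3, in mg/m²)

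| Agent | Levels, high to low | Level 0 | Reference in the rule |
|---|---|---|---|
| Topotecan IV | 2, 1.75, 1.5, 1.25, 1 | 1.5 | 1 (Level -2) |
| Topotecan oral | 3.1, 2.7, 2.3, 1.9, 1.5 | 2.3 | 1.5 (Level -2) |
| Amrubicin | 40, 35, 30, 25 | 40 | 40 (Level 0) |

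The levels rebuild from the protocol's starting doses and steps: 1.5 ± 0.25k and 2.3 ± 0.4k for k = 0, 1, 2, and 40 − 5k for k = 0 to 3.

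**Step 1: apply the rule to every ordered pair of nominal levels.** Five levels give 5 × 4 / 2 = 10 downward and 10 upward pairs; four levels give 4 × 3 / 2 = 6 of each.

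- Reduction: dose < reference and dose < previous dose.
- Increase, as printed: dose > reference and dose < previous dose.

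| Result | Topotecan IV | Topotecan oral | Amrubicin |
|---|---|---|---|
| Downward pairs counted as reductions | 0 of 10 | 0 of 10 | 6 of 6 |
| Downward pairs meeting the increase wording | 6 of 10 | 6 of 10 | 0 of 6 |
| Upward pairs counted as increases | 0 of 10 | 0 of 10 | not applicable (no level above 0) |

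The six downward topotecan pairs that meet the increase wording are +2 to +1, +2 to 0, +2 to -1, +1 to 0, +1 to -1 and 0 to -1. IV example: 1.25 > 1 and 1.25 < 1.5, so a step from 1.5 to 1.25 qualifies.

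**Step 2: read the second clause charitably**, as higher than previous for increases. Increases become 10 of 10 upward pairs for each topotecan form. Reductions stay at 0 of 10, because the reference has not moved: 1 is not below 1, and every other IV level is above it.

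**Step 3: allow for actual doses.** SAP Table 7.4.1-1 says the topotecan dose "is defined as Total Dose administered (mg) / Most recent BSA", so analysed doses will not sit exactly on the levels.

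- *Level -1.* The bands in Table 7.4.2.3-1 are 1.125 to <1.375 (IV) and 1.7 to <2.1 (oral). Both lie wholly above the references of 1 and 1.5. No dose in a Level -1 band can be a reduction.
- *Level -2, oral.* Assume BSA from 1.40 to 2.20 m² in steps of 0.01 (81 values) and doses rounded to 0.25 mg, as the protocol specifies. Then round(1.5 × BSA)/BSA is below 1.5 at 38 of 81 values (39 if ties round down). For a nominal 1.9, the figure is 0 of 81, with a lowest value of 1.82. Whether an oral Level -2 dose counts is thus decided by capsule rounding.

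**Step 4: check what else uses the rule.** The relative dose intensity formula for IV topotecan contains "21) x 7.5 / 21] x 100". Its constant is 5 × 1.5 = 7.5; the others are 5 × 2.3 = 11.5 (oral) and 3 × 40 = 120 (amrubicin). All are built on Level 0, so that measure is independent of this definition, as is cumulative dose.

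**Step 5: test a band-based rule.** With a reduction or increase defined as a move to a lower or higher band of Table 7.4.2.3-1, nominal levels give 10 of 10 downward and 10 of 10 upward pairs for each topotecan form, and 6 of 6 downward for amrubicin.

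**The case against.** The strongest reply is that this is a drafting slip in a descriptive table. Table 7.4.2.3-1 already assigns levels, a programmer could fill the level rows from it, reasons come from the Dose Change CRF page, and by-subject listings would expose an empty row. No programmer would code a step down as an increase.

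Much of that is fair on weight. The 6 of 10 figure shows what the literal text does, not what is likely to be programmed. The zero for reductions is exact only at nominal levels. With doses in mg per BSA some Level -2 doses will count, so the row for any reduction need not be empty. But the sentence is the SAP's definition of a reduction, and nothing says the table or the CRF page overrides it. The Level -1 result needs neither nominal doses nor the literal reading of the second clause.

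Amrubicin is also not a perfect benchmark. With a reference of exactly 40, a dose of 39.8 after 40.1 is a reduction, although Table 7.4.2.3-1 puts both in Level 0. That stands, and it is a further reason to use the bands for all three agents.

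A smaller repair exists: use Level 0 as the topotecan reference with a direction-specific comparison. It captures 7 of 10 downward and 7 of 10 upward topotecan pairs. It misses step-downs that stay at or above Level 0 and step-ups that stay at or below it. The choice between the repairs is the sponsor's, but it has to be stated.

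**Conclusion.** The definition is wrong as written and should be corrected. At nominal levels it counts 0 of 10 topotecan reductions in either form, against 6 of 6 for amrubicin. For actual doses the planned topotecan row for reductions to Level -1 is empty, and inclusion of oral Level -2 doses depends on rounding (about half, 38 of 81, on the assumed BSA grid; the exact share is illustrative). The one-directional second clause is a separate error that removes true increases.

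The consequence is confined to the descriptive dose-modification counts for topotecan and their comparability with amrubicin. Cumulative dose, relative dose intensity, OS, PFS, ORR and the sample size are untouched.

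**What to change.** Reconcile the definition in SAP 7.4.2.3 with Table 7.4.2.3-1, using one logic for all three agents:

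- **Reduction:** a non-zero dose in a lower band than the previous non-zero dose.
- **Increase:** a non-zero dose in a higher band than the previous non-zero dose.
- Keep the dosing-error exclusion for oral topotecan.
- State whether step-downs that remain at or above Level 0 (+2 to +1, +2 to 0, +1 to 0) count as reductions. The band rule counts them unless they are excluded.
- State how a further drop within the open-ended lowest IV and amrubicin bands is handled, since a band rule would not register it.

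Two minor checks on the table while it is open. Oral doses below 1.3 mg/m² have no band; only doses below the protocol minimum would reach that gap, since rounding moves a dose by at most 0.125/1.40 = 0.09 mg/m² on the BSA range above. The IV boundary between Levels +1 and +2 is printed as 1.825, while (1.75 + 2)/2 = 1.875; every other boundary between adjacent levels is the midpoint. Nominal doses are classified correctly either way.

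The cost is SAP wording and a small programming change before the exposure tables are produced. No data collection changes, and the correction affects how doses are counted, not any dose given.

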7.5 Efficacy

7.5.1 Overall Survival

7.5.1.1 Primary Analysis

The distribution of OS will be compared in two randomized arms at the interim and final analyses via a two-sided, log-rank test stratified by baseline stratification factors, as entered into the IVRS.

The hazard ratio (HR) and the corresponding 100(1- α)% CI (adjusted for the interim) will be estimated in a stratified Cox proportional hazards model using randomized arm as a single covariate.

The OS curves for each treatment group will be estimated using the Kaplan-Meier (KM) product-limit method. Two-sided, 95% confidence intervals for median OS will be constructed based on a log-log transformed CI for the survivor function S(t)¹⁰.

Based on the availability of the data, survival rates at 6, 12, 18, 24, 36, 48 months and at 5 year will also be estimated using KM estimates on the OS curve for each randomized arm. Minimum follow-up must be longer than timepoint to generate the rate. Associated two-sided 95% CIs will be calculated using the Greenwood's formula¹¹ for variance derivation and on log-log transformation applied on the survivor function S(t)

The status of subjects who are censored in the OS Kaplan-Meier analysis will be tabulated for each treatment group using following categories:

- on-study (on-treatment and not progressed, on-treatment progressed, in follow-up);
- off-study: (lost to follow-up, withdraw consent, etc.).

Unless otherwise specified, the primary population will be the all randomized population.

